11.0 Statistical Plan

11.1 Statistical Analysis Plan

Participants' basic demographic and baseline clinical measurements will be summarized using descriptive statistics. Those summarizations will be based on all patients as well as on patients within each group. This study has several main groups of outcome variables, which reflect several different domains of patient's mental health. The first group is the emotion thermometer (which has five sub-scales), the second is the somatic symptom scale (SSS-8), the third is the Patient Health Questionnaire (PHQ-9), and the fourth is the Generalized Anxiety Disorder questionnaire (GAD-7), which measures participants' anxiety. All the above outcome variable groups are based on questionnaires using Likert-scale questions to take the measurements, and each group may involve multiple sub-dimensions. Both the intervention group and the control group have repeated measures of the outcomes as shown in Figure 1. Graphical methods (such as the line plot of mean/SD values vs. time) will first be used to illustrate the mean and standard deviation values of the mode, depression, and anxiety scores through the time for both groups. These methods will help us detect the patterns of how the scores change over time (within-group change) and how the scores differ between groups. We will further use the linear mixed-effect model for repeated measures to analyze the within-group and between-group differences. Every sub-dimension will be analyzed individually, but we will also analyze the composite score for the dimensions. For the patients in the control group this study involves two stages (week 1-12 and week 13-20), and at the end of the 12th week, they can join the intervention group. This setting will allow us to study the effect of the intervention on the control group alone. For this part of analyses, linear mixed-effect models will be set up with the stage serves as an indicator variable in the model. The comparison of outcome variables between certain time points will also be done using paired tests. We will further investigate the possible factors that might affect the change of outcome variables over time. The factors are gender, race, marital status, time from cancer diagnosis (first 3 months, 3-6 months, more than 6 months) and cancer stages. This part of analyses will mainly be focused on the intervention group and the above factors will be examined in the linear mixed-effect models. All analyses will be performed using statistical software SAS version 9.4 or higher (SAS Institute, Cary, NC, USA) and the statistical significance level to be used is 0.05.

11.2 Sample size considerations:

We plan to enroll a total of 60 participants in the study – with 40 participants in the intervention group and 20 participants in the control group (2:1 ratio). This sample size is mainly determined by the capacity of the workshop. With this sample size we are able to detect a standard effect size (the mean difference measured in common standard deviation) of 0.45 with at least 80% statistical power (using two-sample repeated measure ANOVA model, assuming four time-points, and the within-patient auto-correlation being 0.2) .

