9.2 Design

The focus of this study is to determine the difference in mental health parameters following the participation of cancer patients in a creative writing workshop. Participants will be randomized within strata formed by cancer type in order to assure that these potentially important confounding variables are balanced across groups. Patients will be enrolled on a rolling basis over a four to five-month period, allowing patients in intervention arm to participate in 2-3 months workshops (workshops would be held once every 2 weeks). Patients in control arm will be provided a book (*Writing Down Bones* by Natalie Goldberg) about creative writing and will be asked to do activities for 1.5 hours every 2 weeks. After three months, control group participants can join creative writing workshops at their discretion for the remaining period for writing workshops. Both group members will receive follow up surveys twice a month for two months at the completion of the participant's two-month study period.

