9.4 Endpoints:**9.4.1 Primary endpoints:**

- Mood scores before (at baseline) and after intervention (after completion of entire sessions - this may vary as some patients may not be able to complete six sessions). A validated Emotional Thermometer Scales will be used to predict changes in parameters pre and post-intervention.
- Severity of depression and anxiety symptoms before and after intervention between two groups. Validated Depression and Anxiety questionnaires will be used to predict changes, the PHQ-9 and GAD-7 respectively.

9.4.2 Secondary endpoints:

[figure not shown]
- Mood and symptoms before and after at least 2 sessions of intervention.
- Self-reported somatic symptoms pre and post intervention in two groups. We will use the Somatic Symptom Scale – 8 (SSM-8) to quantify somatic symptom burden.
- Difference in scores and symptoms between various genders.
- Difference in scores and symptoms between patients living alone versus with family.
- Difference in scores and symptoms in different cancer types.
- Difference in scores and symptoms versus number of classes attended.
- Differences between individual mood scores for patients in the control group who later switch to intervention group and attend at least one session
- Mood and symptom scores up to 2 months after completion of the study.

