10.0 STUDY PROCEDURES

10.1 Methods: After enrollment as above, co-investigators of this study or the assigned coordinator will be doing the consent. Patient will be randomized to intervention and control arms in a 2:1 ratio. The intervention arm will receive a dedicated workshop for one and a half hours every 2 weeks. We aim to start a 6 month long program with weekly creative writings workshops, and patient enrollment in the study will continue through the 1st 4.5 months of the 6 month period so that the last enrolled patient could complete 2 classes per month for two months. Each patient will be asked to attend at least two classes per month for a total of two months. These workshops will be held at Hershey Medical Center (HMC). At the initiation of the study along with consent we will collect baseline scores in both groups for each parameter as below. Somatic Symptom Burden (SSM-8 - Figure 2 - reference section), depression symptoms using PHQ-9 (Figure 3 – reference section), and anxiety symptoms using GAD-7 (Figure 4 – reference section) will be collected monthly and following intervention completion.

We will collect mood scores pre and post each session. We will use Emotional Thermometer Scale (EMS) from [name] (Feb. 2010), diagram for scales is shown in figure 1. Please see supplementary index for a letter of permission to use from [name]. We will give the Thermometer scales and collect scores pre and post each session and also collect scores pre and post completion of entire course. Control group will do EMS on monthly basis along with other parameters. At the end of the study we will review all participants' medical charts to count view the number of emergency room visits and hospitalizations each participant experienced during the study period. These will be further broken down in categories based on cancer

Institutional Review Board

related vs non-cancer related visits. We will also review their most current cancer disease status after completion of the workshops and categorize whether their status is considered to be stable, progressing, or in remission. Both groups will also receive follow up mood and symptom surveys twice a month for up to 2 months after completion of the participant's two to three month study period.

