10.2 Clinical Covariates: Detailed clinical covariates will be obtained from questionnaires and medical record review including demographics (age, gender, race), cancer type and stage, psychiatric history, chemotherapy regimen and medication use.

10.3 Creative Workshop: Write from Heart: This workshop for cancer patients usually lasts one and a half hours and is broken into several parts. Usually beginning with inspirational quotes or passages from writings of respected authors, to shift mood and illuminated deeper thought and reflection. The next phase of the class consists of sharing a beautiful or whimsical object handed person to person or placed in the middle of the table to stimulate both curiosity and the senses. When participants are able to relax fully, in tranquil and focused surroundings the imagination easily transforms a bright polished stone or a glass heart with inner fractures into a metaphorical image. The technique of journaling is also encouraged in class, as a way to promote inner awareness to strengthen writing skills and to guide students to reach for their own comfort and consolation, when not in class. Within our setting, it is normal, though not mandatory that writing may lean toward the cancer experience. At the end of each series, students would have learned how to trust their artistic instincts, connect more courageously with

Institutional Review Board

the world of their emotions and transform their fears and revelations about cancer into words on the page.

10.4 Emotional Thermometers Scale: The Emotion Thermometers tool is a simple rapid modular screening tool for detection and monitoring of emotional disorders in clinical practice. It was created by [name] J Mitchell and has a simple visual-analogue design. It is easy for most patients (including older people) to understand, quick to administer and simple to score. We have already got permission from [name] J Mitchell for royalty free usage of this scale for 2 years starting from Aug, 2016 till Aug 2018. We will be getting permission from him to extend the usage for an additional 1-2 years.

10.5 Survey of Depression and Anxiety symptoms: For anxiety, we will use Generalized Anxiety Disorder 7-item (GAD-7) validated scale by Robert Spitzer et al. For depression we will use Patient Health Questionnaire 9-item (PHQ-9) validated scale by Robert Spitzer et al. Both of these scales do not require any permission for reproduction, display, distribution or usage.

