22.0 TABLES and FIGURES for the STUDY**Table 1: DEMOGRAPHICS**

Participant	1	2	3	4	5	6	7...
Serial Number							
Alphanumeric code							
Medical Record Number							
Gender							
Age							
Living Alone vs with family/caretaker							
Primary Cancer Type							
Cancer Stage							
ECOG Performance Status							
Enrolled in the Exercise Study							
Regular exercise on or off the exercise study- >30mins three times a week							
Current Treatment (Surgery, Radiation, Chemo)							
Disease status at completion of study (Stable, Progression, Remission)							
Psychiatric history (previous diagnoses or hospitalizations)							
Current Psychiatric Medications							

Figure 1: Emotion Thermometer Score (ETS)

Emotion Thermometers 5 items+help

Instructions: In the first four columns, please mark the number (0-10) that best describes how much emotional upset you have been experiencing in the past week, including today. In the last column please indicate how much you need help for these concerns.

1. Distress	2. Anxiety	3. Depression	4. Anger	5. Need Help
 An orange thermometer with a scale from 0 to 10. The bulb at the bottom is orange and the stem is orange. The top of the stem has three orange radiating lines. The number 10 is at the top and 0 is at the bottom.	 A green thermometer with a scale from 0 to 10. The bulb at the bottom is green and the stem is green. The top of the stem has three green radiating lines. The number 10 is at the top and 0 is at the bottom.	 A blue thermometer with a scale from 0 to 10. The bulb at the bottom is blue and the stem is blue. The top of the stem has three blue radiating lines. The number 10 is at the top and 0 is at the bottom.	 A red thermometer with a scale from 0 to 10. The bulb at the bottom is red and the stem is red. The top of the stem has three red radiating lines. The number 10 is at the top and 0 is at the bottom.	 A grey thermometer with a scale from 0 to 10. The bulb at the bottom is grey and the stem is grey. The top of the stem has three grey radiating lines. The number 10 is at the top and 0 is at the bottom.
Extreme				Desperately
None				Can manage by myself

Are you already getting help for these problems? N/A No Yes Do you want further help for these problems? No Yes

Alex J Mitchell © 2013

Figure 2: Somatic Symptom Scale

Somatic Symptom Scale – 8 (SSS-8)

During the past 7 days , how much have you been bothered by any of the following problems?					

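### Section 11.1 names a mixed model for the between-arm comparison but specifies neither the baseline score nor the cancer-type randomisation stratum as a term

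*Combined protocol and SAP*

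**What the plan says.** Section numbers follow the first of the three protocol versions in the file; the other two carry the same statistical text under 12.1 and 13.1.

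- **Model.** Section 11.1 states: "We will further use the linear mixed-effect model for repeated measures to analyze the within-group and between-group differences". It gives no fixed effects, no handling of baseline and no covariance structure for that comparison.
- **Terms named for other analyses.** A stage indicator belongs to the control-only, two-stage analysis. A factor list belongs to an analysis of change over time, run mostly within the intervention arm: "The factors are gender, race, marital status, time from cancer diagnosis (first 3 months, 3-6 months, more than 6 months) and cancer stages". Baseline score and cancer type are in neither. Cancer stage is a different variable.
- **Stratum.** Section 9.2: "Participants will be randomized within strata formed by cancer type in order to assure that these potentially important confounding variables are balanced across groups". Cancer type is collected (section 10.2: "cancer type and stage, psychiatric history, chemotherapy regimen and medication use"; section 22.0, Table 1: "Primary Cancer Type"). Otherwise it appears only as a secondary comparison in sections 4.2 and 9.4.2.
- **Baseline.** Section 10.1: "At the initiation of the study along with consent we will collect baseline scores in both groups for each parameter as below".
- **Endpoint.** Section 9.4.1 describes the mood endpoint as baseline against the end of the course, and the symptom endpoint as "Severity of depression and anxiety symptoms before and after intervention between two groups".
- **Power.** Section 11.2 claims at least 80% power for 0.45 SD with 40 and 20 patients, "assuming four time-points, and the within-patient auto-correlation being 0.2".

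**The concern.** When randomisation is balanced within strata and the strata are prognostic, the arm difference varies less than an analysis without them assumes. The reported standard error is then too large, and precision is lost that the design had already secured.

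Baseline raises a different problem. Before-and-after wording fits a covariate-adjusted model, a model with baseline as an outcome row constrained equal across arms, or a contrast of change scores. The first two are close to equivalent. The third is much weaker when the correlation is low, and section 11.2 assumes a low one. An unwritten model leaves that choice open until data are in hand.

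At stake are some precision in a 60-patient trial and a primary test fixed before outcomes are compared by arm.

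**Working it through.** **Inputs.** From section 11.2: effect 0.45 SD, 40 against 20 patients, four time-points, correlation 0.2. From section 11.1: significance level 0.05. Assumed: two-sided test, complete data, unit variance, four post-baseline scores plus a separate baseline. Section 11.2 does not say whether baseline is one of the four, so three post-baseline scores are also shown.

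**Formulas.** Let V be the variance of the mean post-baseline score and c its covariance with baseline.

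- Ignoring baseline: V, 58 df.
- Adjusted for baseline: V − c², 57 df. Chance baseline imbalance multiplies this by 1 + 1/57.
- Unconstrained change score: V + 1 − 2c, 58 df.
- SE = √(variance × (1/40 + 1/20)) = √(variance × 0.075). Power is from the non-central t distribution.

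**The plan's own figure.** Under AR(1) 0.2, V = [4 + 2(3×0.2 + 2×0.04 + 0.008)]/16 = 5.376/16 = 0.336. SE = √(0.336 × 0.075) = 0.1587, and 0.45/0.1587 = 2.835. Power is 79.6% (80.9% by the normal approximation), which matches section 11.2 approximately. Under compound symmetry (CS) 0.2, V = (4 + 12×0.2)/16 = 0.400 and power is 72.4%, which does not.

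**Baseline.** Under AR(1) 0.2, c = (0.2 + 0.04 + 0.008 + 0.0016)/4 = 0.0624. The adjusted variance is 0.336 − 0.0039 = 0.3321, and the change-score variance is 0.336 + 1 − 0.1248 = 1.2112. Under CS 0.2, c = 0.2, giving 0.36 and 1.00.

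| Post-baseline scores, structure, correlation | Ignoring baseline | Adjusted | Adjusted, chance imbalance | Change score |
|---|---|---|---|---|
| 4, AR(1), 0.2 | 79.6% | 80.0% | 79.4% | 31.2% |
| 4, CS, 0.2 | 72.4% | 76.8% | 76.1% | 36.6% |
| 3, AR(1), 0.2 | 69.2% | 69.8% | 69.1% | 30.1% |
| 3, CS, 0.2 | 65.7% | 69.6% | 68.9% | 34.7% |
| 4, AR(1), 0.5 (assumed) | 61.4% | 66.3% | 65.5% | 35.2% |
| 4, CS, 0.5 (assumed) | 53.4% | 75.1% | 74.4% | 53.4% |
| 4, AR(1), 0.7 (assumed) | 50.1% | 64.4% | 63.6% | 44.3% |
| 4, CS, 0.7 (assumed) | 45.1% | 85.7% | 85.1% | 75.1% |

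**Final score alone.** The variance is 1, so SE = √0.075 = 0.2739 and power is 36.6%. With baseline adjustment it is 36.5% under AR(1) 0.2, where baseline and the fourth score correlate only 0.2⁴ = 0.0016, and 37.8% under CS 0.2.

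**Stratum.** This was simulated with 20,000 trials per setting: 60 patients in equally likely strata, 2:1 permuted blocks of 3 or 6 within stratum (block size is not stated), AR(1) 0.2, and the mean of four scores regressed on arm and baseline with or without stratum. The share of residual variance due to cancer type is an assumption; the documents give none.

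| Share explained | Power change, 3–6 groups (points) | Power change, 15 sparse strata (points) | Coverage of 95% interval without stratum (3–6 groups) |
|---|---|---|---|
| 0% | −0.1 to −0.8 | −3.1 to −5.3 | about 95% |
| 5% | +0.9 to +1.4 | −1.4 to −3.2 | about 95.5% |
| 10% | +2.4 to +3.0 | −1.4 to +0.2 | about 96% |
| 20% | +5.4 to +5.8 | +2.1 to +3.4 | about 97% |

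The widening from omission is 1/√(1 − share) − 1, or 2.6%, 5.4% and 11.8% at 5%, 10% and 20%.

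**The case against.** The strongest reply is that little is lost. At the correlation structure that recovers section 11.2, baseline adjustment is worth 0.4 points, and slightly less than nothing once chance imbalance is charged. Omitting the stratum costs efficiency, not validity. The larger gains need correlations or a prognostic strength that no document gives. All of that stands.

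It is also fair that powers for an average over follow-up do not describe the mood endpoint of section 9.4.1, which is taken after the course. For that contrast, power is about 37% whatever is done with baseline. The number of usable points is uncertain too. With monthly PHQ-9 and GAD-7 and two months of requested participation, two post-baseline points are plausible. AR(1) 0.2 then gives 55.0% ignoring baseline and 56.0% adjusted.

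Three stronger readings are tempting and are not supported:

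- **That the plan will use change scores, or will ignore baseline.** It states neither. A mixed model with baseline among the repeated measures could handle it implicitly. The fault is that the plan does not say.
- **That omitting the stratum inflates false positives.** The simulated coverage is at or above the nominal level, to within simulation error.
- **That, with the sample size set by workshop capacity, any extra precision must come from the model.** Capacity limits workshop places, but controls read a book on their own and join later only if they choose. At AR(1) 0.2, 30 controls would give 88.7% power and 40 would give 92.9%, though slow accrual may limit this.

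**Conclusion.** The point holds as a gap in specification with a cheap remedy. It should be fixed, but it does not threaten the validity of the trial. The text is clear on the omission; confidence in its size is moderate.

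The case for the stratum is that the analysis should follow the randomisation. Its benefit depends entirely on how prognostic cancer type is, and it reverses if many sparse strata are entered uncombined. The case for baseline is mainly pre-specification: writing it down closes off the one reading that would do real damage at correlation 0.2. The precision gain depends on a correlation structure the plan leaves unstated.

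The calculation also shows that the power claim in section 11.2 comes close only for an average over four scores, while section 9.4.1 points to the end of the course. Which of these is tested matters far more than either covariate.

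**What to change.** In section 11.1, state the primary between-arm model as post-baseline scores on arm, time, arm-by-time, baseline score of the same scale (or a constrained-baseline equivalent), and cancer type combined into about 3 to 6 groups. Fix the combining rule before outcomes are compared by arm; it is needed because section 7.3 admits any cancer and the number of strata is not given.

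Also state:

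- **Assessment times.** Use times common to both arms and before controls may join the workshops. Section 10.1 has thermometer scores around each session in the intervention arm but monthly in controls. Sections 9.2, 10.1 and 11.1 differ on when controls may join (three months; two months or four sessions; end of week 12), and these must be reconciled.
- **Contrast.** Name either the average over post-baseline times, whose power comes close to section 11.2, or the end-of-course score of section 9.4.1, and make section 11.2 match. With an interaction in the model, the arm coefficient alone refers to one reference time.

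**Cost.** A few sentences and a few lines of SAS, with no new data. Baseline uses one degree of freedom, about 0.2 points at AR(1) 0.2 after chance imbalance. If cancer type explains nothing, 3 to 6 groups cost under 1 power point, against about 3 to 5 points for 15 sparse uncombined strata.

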2.2 Primary Sponsor: Penn State Hershey Cancer Institute

3.0 PROTOCOL ABSTRACT

The primary purpose of this study is to determine whether creative writing in newly diagnosed cancer patients and those with recent progression in their disease will have a positive impact on their mental health. Using a randomized controlled trial approach, emotion thermometers will be employed to evaluate participants' responses on a number of domains, such as anxiety, depression, despair, and anger along with a series of survey questions to monitor changes in depressive and anxiety symptoms. Open-ended survey questions will be used to capture how a creative writing intervention impacts participants' experience of their illness. [name]'s *Write from the Heart* program focuses more on creative writing rather than cancer focused topics. Patients in the intervention arm will complete – one and a half hour group sessions every two weeks over the span of 3 months. Participants in the active control arm will be provided a book (i.e., *Writing Down Bones* by Natalie Goldberg) about creative writing and will be asked to do activities for 1.5 hrs every 2 weeks for a period of 2-3 months.

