6.0 RATIONALE AND HYPOTHESIS

6.1 RATIONALE:

Cancer generates an increased sense of distress than non-malignant diseases with poor prognoses (Mishel et al., 1984). Persistent mental distress for prolonged periods leads to anxiety and depression. The rate of depression in cancer patients is thought to be up to three times higher than in the general population (Linden et al., 2012). Depression leads to a poorer quality of life (QOL) and affects patient outcomes, with depression resulting in higher rates of mortality in cancer (Colleoni et al., 2000, Pinquart et al., 2010). A meta-analysis revealed that minor or major depression increases mortality rates by up to 39%, and that patients displaying even few depressive symptoms may be at a 25% increased risk of mortality (Satin et al., 2009). The impact of mood and mental wellbeing on cancer progression is considered important by doctors and patients, with >70% of oncologists and 85% of patients believing that mood affects the progression of cancer (Lemon et al., 2004). Our previous data as mentioned before shows that creative writing is feasible and needs to be further studied to understand the effect of group therapy with focused workshop in newly diagnosed or patients with recent recurrence. In addition, we observed that the emotional thermometer scale was not enough to capture the mood of the patients. For example, some patients felt significantly better after attending these sessions and were able to cope with their symptoms but the emotional scale did not reflect that benefit.

6.2 HYPOTHESIS:

This study aims to look at the impact of participating in creative writing workshop group *Write from the Heart*, on cancer patients' emotional well-being. Keeping previous studies in mind, a

Institutional Review Board

professional writer will conduct the workshops, which will enhance the participant's ability to express and enhance their awareness. We anticipate that participation in the workshop will result in a positive effect on the parameters being studied, enabling patients to cope with their illness/cancer better. We hypothesize that group sessions of creative writing workshop could be better than individual sessions.

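### The workshop arm is treated in shared classes, but 11.1 names no class-level term and the 80% power in 11.2 holds only if all 60 patients are independent

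*Combined protocol and SAP*

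**What the plan says.** **Delivery.** The abstract (3.0) describes the intervention as "one and a half hour group sessions every two weeks over the span of 3 months". Section 10.1 asks each patient for a two-month minimum; that difference in length does not affect this point. Section 6.2 says a professional writer leads the workshops, and section 10.3 describes an object shared around a table. The group format is itself part of the hypothesis: "We hypothesize that group sessions of creative writing workshop could be better than individual sessions". Controls read and write on their own from a book (10.1, 10.6).

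**Analysis.** Section 11.1: "We will further use the linear mixed-effect model for repeated measures to analyze the within-group and between-group differences". It lists no random effects and mentions no class, session or cohort. On the test level, "the statistical significance level to be used is 0.05"; sidedness is not stated.

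**Power.** Section 11.2 plans 40 workshop and 20 control patients and puts the power for a 0.45 SD difference at 80% or more. The basis it gives is: "using two-sample repeated measure ANOVA model, assuming four time-points, and the within-patient auto-correlation being 0.2". That is the only correlation given. Class size, number of classes, intra-class correlation and design effect appear nowhere. The other two protocol versions in the file carry the same statistical text.

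**The concern.** Patients who sit in the same class share a leader, a room, a discussion and each other. If that shared experience moves mood, as the hypothesis proposes, their scores will tend to move together. Controls share nothing of the kind. The trial is therefore partially nested: there are clusters in one arm and none in the other.

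A repeated-measures model with the patient as its only unit takes account of correlation between one patient's scores, but not between classmates. With positive class correlation, the workshop mean is less precise than 40 independent patients would make it. The planned interval for the difference between arms would then be too short, the 5% test would reject too often, and the power would be lower than stated. This affects the main randomized comparison on all the primary scales in 9.4.1 (Emotion Thermometers, PHQ-9, GAD-7), and the error leans towards claiming a benefit.

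**Working it through.** **Inputs from the documents (11.1, 11.2).** 40 vs 20 patients; difference 0.45 SD; four time points; within-patient autocorrelation 0.2; alpha 0.05.

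**Assumed here, because the documents are silent.** A two-sided test; AR(1) structure; class size m; intra-class correlation ρ of the patient's mean score.

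**Step 1. Reproduce the stated power with independent patients.**

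- Variance of a patient's mean of four scores: v = [4 + 2(3×0.2 + 2×0.04 + 0.008)]/16 = 5.376/16 = 0.336.
- SE = √(0.336 × (1/40 + 1/20)) = √0.0252 = 0.1587.
- Power = Φ(0.45/0.1587 − 1.960) = Φ(0.875) = 80.9%; noncentral t with 58 df gives 79.6%.
- Effect detectable at exactly 80% power: (1.960 + 0.842) × 0.1587 = 0.445 SD, against 0.45 stated.

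So the claim reproduces with no design effect and almost no room. Compound symmetry at 0.2 (v = 0.40) gives 73.8% two-sided. One-sided tests give 83.0% (compound symmetry) or 88.3% (AR(1)). The two-sided AR(1) reading is the one that lands on 80%, and it is used below.

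**Step 2. Allow for class correlation in the workshop arm only.**

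- Var = A + B, with A = 0.336 × [1 + (m − 1)ρ]/40 and B = 0.336/20 = 0.0168.
- Example, m = 10 and ρ = 0.05: A = 0.336 × 1.45/40 = 0.01218; SE = √0.02898 = 0.1702, which is 1.07 times the independent SE; power = Φ(0.45/0.1702 − 1.960) = 75.3%.

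**Step 3. False-positive rate of the unadjusted test.**

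- Rate = 2P(Z > 2.002 × naive SE/true SE). The naive SE uses the pooled variance expected under clustering, with the workshop-arm sample variance equal to v[1 − (m − 1)ρ/39].
- Same example: pooled factor = (39 × 0.9885 + 19)/58 = 0.9922; naive SE = 0.1587 × √0.9922 = 0.1581; rate = 2P(Z > 1.860) = 6.3%.
- This formula returns about 4.5% with no clustering, so it errs slightly low.

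**Step 4. Small-sample degrees of freedom.**

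- With k = 40/m classes, df = (A + B)²/[A²/(k − 1) + B²/19].
- Example, m = 13 and ρ = 0.10: A = 0.01848, k = 3.08, df = 6.9.

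| m | ρ | True SE / independent SE | False positives | Power (normal) | df | Power (t) | Interval width vs independent |
|---|---|---|---|---|---|---|---|
| 8 | 0.02 | 1.02 | 5.1% | 79% | 18 | 75% | 1.07 |
| 8 | 0.05 | 1.06 | 5.9% | 77% | 17 | 72% | 1.11 |
| 8 | 0.10 | 1.11 | 7.3% | 72% | 15 | 66% | 1.19 |
| 13 | 0.02 | 1.04 | 5.5% | 78% | 11 | 70% | 1.14 |
| 13 | 0.05 | 1.10 | 6.9% | 74% | 9 | 64% | 1.24 |
| 13 | 0.10 | 1.18 | 9.4% | 67% | 7 | 54% | 1.40 |

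**Step 5. Lower end.** With m = 5 and ρ = 0.01 the design effect is 1.04, the SE rises by under 1% and power is 80.4%. That is negligible.

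**The case against.** **The harm is conditional.** A reader might infer that the intervals are too narrow and the power overstated as a matter of fact. The documents do not support that. Both need a positive class correlation, and neither its value nor a class size is given. This objection stands. The direction is fixed for any positive correlation, but the size is not.

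**The plan never says patients are independent.** Section 11.1 lists no random effects and excludes none, so this is an omission, not a declared assumption. That also stands for the analysis model. It does not help the power figure, whose stated inputs contain only a within-patient correlation.

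**Fixed cohorts do not match the design.** Enrolment is rolling (9.2), classes run weekly while each patient attends about every second week (10.1), and controls may later join the same workshops. Classes may be open and overlapping, so the date of a patient's first class would not show who sat together. This rules out a simple nested cohort term as the default, but not the need to address class correlation.

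**Class attendance may not be on file.** Number of classes attended is an endpoint (9.4.2) and thermometers are collected around each session (10.1), so class dates should be obtainable. No attendance record by date is described, however, and the activity log in 10.6 belongs to the controls.

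**Larger figures are possible but weakly supported.** Treating all 40 patients as one class gives 71-46% power and 8-20% false positives at correlations of 0.02-0.10. A single cluster, though, is wholly confounded with arm, and no model term could estimate its variance. Putting the correlation on the single-score scale, with a group effect present at all four time points, gives 65% power at m = 10 and ρ = 0.05. Baseline is collected at consent or in the week before the first session, so it cannot carry a class effect. If baseline is one of the four points, that figure overstates the loss.

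**The sample size would not change.** Section 11.2 says workshop capacity mainly set the number. That is true, but the stated power and the interval would still be wrong if classmates are correlated.

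**Conclusion.** The gap is real and moderate. One arm is delivered in groups, no class-level term is planned, and the 80% reproduces only with 60 independent patients, on a two-sided AR(1) reading that leaves almost no slack. Any positive class correlation makes the unadjusted between-arm interval too narrow and, on that reading, takes power below 80% unless the correlation is very small.

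For assumed classes of 8-13 and correlations of 0.02-0.10 on the patient-mean scale, the 5% test rejects about 5-9% of the time. Power is about 67-79% by normal approximation, or about 54-75% once the degrees of freedom reflect only 3-5 clusters. These are illustrations under stated assumptions, not estimates for this trial.

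**What to change.** **In 11.1:**

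- Record the class dates each workshop patient attends.
- Keep the planned mixed model. Add a sensitivity analysis of the primary between-arm comparisons that allows for class correlation in the workshop arm only. If there are enough classes, use a class or multiple-membership random effect with small-sample degrees of freedom (Satterthwaite or Kenward-Roger). Otherwise, give intervals over a stated range of fixed correlations, for example 0.01-0.10, labelled as assumptions.
- State that an effect common to all classes, such as that of a single writer, cannot be separated from arm by any model term.

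**In 11.2:** replace the single 80% figure with a power range that states the assumed class correlation, class size and within-patient correlation structure, and say whether the test is two-sided.

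**Cost:** one data field and some analysis work. The sensitivity intervals would be wider (about 7-40% if there are only 3-5 clusters, on the assumptions in the table) and the stated power lower. No additional patients. The class dates should be captured while classes are running, since membership may be hard to reconstruct afterwards.
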